## 7.2 General Methodology

### 7.2.1 Statistical Methodology

All summary statistics will be presented by the actual randomization arm. FAS will be the main analysis set used for the analysis.

Descriptive statistics will be used to summarize patient demographics and baseline characteristics, medical history, procedure data, and other relevant study data. Mean and standard deviation, minimum, maximum, and median with the interquartile range (IQR) will be used for continuous

variables. Counts and percentages will be presented for categorical variables. Summary statistics will be reported with the same number of decimal places as original data collected.

Since the study was terminated early, also the primary and secondary endpoints will be analyzed with descriptive statistics without testing formal hypotheses.

For time-to-event analysis, if the number of observed events will be adequate, the Kaplan-Meier plots will be plotted by arm but only with a descriptive purpose. The survival probabilities at each follow-up visit will be calculated using Kaplan-Meier estimator together with 95% confidence intervals (using complementary log-log method) and will be presented in a table by arm for descriptive purpose.

Statistical analysis will be conducted in SAS version 9.4 or above (SAS Institute, Cary, NC).

Any deviations from the SAP will be described and justified in the Clinical Study Report

### **7.2.2 Derived Variables**

Variables to evaluate the primary endpoint, as well as daily AF burden metrics, number of successful and unsuccessful treated AT/AF episodes out of detected episodes, number of delivered therapies per episode, and number of ATP sequences will be derived from the device datasets and will be described in detail in the SPR (ref).

The exposure time (months) for the time to first persistent AF will be computed from the date of randomization to the date of the last device save to disc for patients without persistent AF recurrence or to the date of first recurrence of persistent AF recurrence otherwise  $[(\text{data end} - \text{data in})/30.4]$ .

Variables to evaluate secondary endpoints as all-cause death, cardiovascular hospitalization (HF, AF or other), stroke, TIA or other thromboembolic events and annual rate for all-cause hospitalization will be derived from the adverse event dataset and will be described in detail in the SPR (ref).

The exposure time (months) for the secondary endpoints will be computed from the date of randomization to the date of the notice (follow-up visit or adverse event) for patients without events or to the date of the specific event otherwise  $[(\text{data end} - \text{data in})/30.4]$ .

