11.2. Reporting of Adverse Events

11.2.1. Recording and reporting of Adverse Events

As this is a post market interventional study, we will collect all cardiovascular-related Adverse Event, device-related AE and all SAE.

The reporting requirements for the investigational study site is as below:

Events to Report	Reporting Requirement and Timeframe	Submit to
All SAE, SADE, USADE	Investigator shall report all SAEs, SADEs and USADEs to the Ethics Committee, monitor and Sponsor promptly of their occurrence. (Indian GCP section 3.3.4.3) For reported deaths the investigator shall supply any additional information (e.g., autopsy report and terminal medical reports.) (Indian GCP section 3.3.4.5) It is recommended for investigator to report all SAEs, SADEs and USADEs to the sponsor within 24 hours. It is recommended for investigator to report all SAEs, SADEs and USADEs to EC within 7 working days unless the stricter timeline is required by the EC.	Sponsor Monitor EC
New information that may adversely affect safety of the subjects or the conduct of the study	Investigator shall promptly report new information that may adversely affect safety of the subject or the conduct of the study. (Indian GCP section 3.3.4.4)	EC Sponsor Monitor

All cardiovascular related AEs and device related AEs should be reported immediately but no later than 3 calendar days after investigational site personnel's awareness of the event.

The investigator will report adverse events on the study database (EDC system) as soon as possible upon notification.

Sites are however required to follow their respective Ethics committee requirements for safety reporting as needed (which includes any SAE/ SADE/USADE) while the patient is still on the study, but only Device related AE, Cardiovascular related AE and all SAEs will be collected towards the study. Refer to the Adverse Event eCRF for the information to be reported for each Adverse Event.

In the event of a medical emergency if the investigator requires information from the sponsor, the investigator can contact the Clinical Study Team for details.

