13.2.9. Evaluation of objectives

Time to event analysis will be performed by means of the Kaplan Meier method. Time to event must be calculated as time from enrollment date or the first day in sinus rhythm after enrollment, to the date of event for patients with complications, and time from enrollment date to the last patient information date otherwise (the date of last transmission, date of last follow-up, exit or death date). Difference in time-dependent event between population subgroups will be evaluated using a Cox proportional hazard regression model. The proportionality of the risk will be tested with the Schoenfeld method. Confounding factors will be identified among baseline characteristics and device data eventually collected before inclusion. All outcomes will be evaluated considering confounding factors by means multivariate models or stratification as appropriate. Rates were computed for 100-person years and were compared by means of the Poisson model using the scale deviation parameter to adjust for over-dispersion. Incidence rate ratios (IRRs) with their 95% confidence intervals (CIs) were computed to measure events reductions in the interventional arm. IRRs were also adjusted to account for the effect of potential confounders.

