### 7.1.3 Analysis Sets

The following analysis sets were defined in the CIP:

- The Per Protocol Analysis Set (PP) includes all patients actively enrolled in the study, who signed Informed Consent Form (ICF), fulfilled the inclusion/exclusion criteria and that have one day in Sinus Rhythm at the time of enrollment or after the enrollment.
- The Intention-to-Treat Set (ITT) includes all patients actively enrolled in the study, who signed ICF, and fulfilled the inclusion/exclusion criteria.

Since the study was terminated early with low number of patients enrolled, no significant differences in terms of sample size between the PP and ITT population sets are expected. Moreover, the device data interrogation compliance, due to the COVID-19 pandemic, was far from what expected in the investigation plan. For these reasons the Full Analysis Set (FAS) including all patients randomized into the study and fulfilling the inclusion/exclusion criteria will be used throughout the analysis.

The primary endpoint and the secondary endpoints will be analyzed in the FAS population with descriptive statistics without testing formal hypotheses. For the same reason no analyses on subsets of the FAS as outlined in the study protocol will be performed. In addition, individual subject listings could be generated, if needed.

The randomization arm will be used throughout the analysis.

Information about, patients assigned to the different treatment arm then the arm to which the patient was randomized (i.e. wrong device programming in terms rATP feature), will be reported in the protocol deviation table or listing if needed.

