## 7.4 Handling of Missing, Unused, and Spurious Data and Dropouts

Since the impact of missing data is expected to be small, and only descriptive statistics will be applied no multiple imputation method for missing data is planned. For subjects who are lost to follow-up, the time to event will be censored at the last available contact date.

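### SAP 7.2.2 lets follow-up for the secondary clinical endpoints depend on adverse events and sets no matching cut-off for endpoint events, so rates are overstated wherever exit falls after the last attended visit

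*SAP*

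**What the plan says.** SAP 7.2.2 takes death, cardiovascular hospitalization, thromboembolic events and the all-cause hospitalization rate from one source: they "will be derived from the adverse event dataset". Exposure starts at randomization. It runs "to the date of the notice (follow-up visit or adverse event) for patients without events", "or to the date of the specific event otherwise".

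Protocol 13.2.9 closes event-free time at the latest date with patient information and lists four candidates: "the date of last transmission, date of last follow-up, exit or death date".

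SAP 7.4 adds a third statement: "For subjects who are lost to follow-up, the time to event will be censored at the last available contact date".

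SAP 7.12 explains why formal testing was dropped but does not mention the change of end date. Protocol 13.2.12 asks for departures from the original statistical plan to be described and justified in the final report.

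**The concern.** Events and event-free time reach the analysis by different routes. Protocol 11.2.1 has serious events sent in as they happen: "It is recommended for investigator to report all SAEs, SADEs and USADEs to the sponsor within 24 hours". Event-free time is confirmed only at a visit, and in-office visits are recommended every 6 months. A hospitalization after the last attended visit can enter at its own date, while a patient who stays well over the same period is cut off at that visit. If that patient has some unrelated adverse event, the clock runs on to it.

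This means that being observed for longer partly depends on having something to report. With no tests or hazard ratios planned, the Kaplan-Meier estimates and annual rates by arm are the main secondary results, and an error in person-time passes straight into them.

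**Working it through.** **No stated figure to reproduce.** The documents give no person-time, event count or expected rate for these endpoints. The planned 758 patients do not bear on this point.

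**Step 1. The rules side by side.**

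| Possible end date | Protocol 13.2.9 | SAP 7.2.2, secondary endpoints |
|---|---|---|
| Last follow-up visit | yes | yes |
| Last transmission | yes | not named |
| Exit | yes | not named |
| Death | yes | only as an adverse event |
| Unrelated adverse event | not named | yes |
| Last date on which an endpoint event counts | not stated | not stated |

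Take two patients with the same last visit and the same exit date, both free of the endpoint. Under the SAP rule, the one with a later unrelated adverse event is credited with more follow-up.

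**Step 2. Effect of a gap g between last visit and exit.** Assumptions, none of them in the documents: exponential times, first event only, event rate λ of 6.5 to 30 per 100 patient-years, follow-up T of 12 to 24 months, unrelated adverse events at a = 0.3 per year, and all events in the gap recorded.

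- Mean exposure to event or exit: E = (1 − e^(−λT))/λ
- Mean time lost by an event-free patient, allowing for extension by an unrelated event: L = (1 − e^(−ag))/a
- Rate ratio, SAP rule over exposure to exit: E / (E − e^(−λT) × L)

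With λ = 6.5 per 100 patient-years, T = 12 and g = 2 months: E = 11.62 months, e^(−λT) = 0.937, L = 1.951. The ratio is 11.62/(11.62 − 1.828) = 1.19.

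With λ = 30, T = 24 and g = 2: E = 18.05, e^(−λT) = 0.549. The ratio is 18.05/(18.05 − 1.071) = 1.06.

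| Gap, if every patient has it | Ratio over the assumed range |
|---|---|
| 0 | 1.00 |
| 1 month | 1.03 to 1.09 |
| 2 months | 1.06 to 1.19 |
| 3 months | 1.10 to 1.30 |
| 6 months | 1.20 to 1.82 |

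If only 15% of patients have the gap, the loss term is multiplied by 0.15. The ratio is then 1.01 to 1.04 for 3 months and 1.03 to 1.07 for 6 months.

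**Step 3. Effect of missed visits.** This is a simulation with assumed inputs: exit 2 to 24 months after randomization, visits every 6 months, 25 hospitalizations and 20 other adverse events per 100 patient-years, death at 6.5% per year, and serious events captured to exit.

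| Attendance | First hospitalization | Death |
|---|---|---|
| 100% | 1.00 | 1.00 |
| 90%, including final visit | 1.02 | 1.03 |
| 80% of visits, 85% final | 1.04 | 1.04 to 1.05 |
| 70% | 1.10 | 1.11 |
| 60% | 1.16 | 1.17 to 1.18 |

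**Step 4. What the calendar allows.** SAP section 5 places final visits of ongoing subjects in June and July 2021 and termination in August; SAP section 3 sets database lock at 1 September. If exit is dated at termination, the gap is close to nil for a visit on 31 July. For a visit on 1 June it is two months to the start of August, or three to its end. If the final visit is the exit, the gap is zero.

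**Step 5. Against sampling error.** With 75 patients and a mean exit of 13 months, (2 + 24)/2, there are 75 × 13/12 = 81 patient-years. At 6.5% per year that gives about 5 deaths. The exact Poisson 95% interval for 5 events is 1.6 to 11.7, or 0.3 to 2.3 times the estimate.

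**The case against.** Several points on the other side stand:

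- The protocol's rule is not simply exit or death. It is the latest of four dates, and the SAP keeps one of them, last follow-up.
- The death date is not lost. Death is a serious adverse event, so the adverse-event option can carry it.
- A final visit was scheduled for ongoing subjects. Data after withdrawal of consent are not recorded, and SAP 7.4 already covers loss to follow-up.
- The recommended reporting time concerns speed. It does not show complete capture in patients who stop attending. If late events are also missed, numerator and denominator shrink together and the bias shrinks with them.
- The SAP defers variable detail to a separate programming document that is not public, and the end date may be settled there. The SAP also says only the date of the notice; reading this as the latest such date is natural but is an inference.

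A reader might take the SAP's remark that "the device data interrogation compliance, due to the COVID-19 pandemic, was far from what expected" as evidence of poor attendance. It concerns device downloads and gives no figure for clinic visits. A reader might also infer a bias between arms, because investigators know the assignment. The rule is the same in both arms, and nothing in the documents shows differential reporting.

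None of this removes the problem in the text: an end date that adverse events can move, no matching cut-off for events, and a rule that differs from SAP 7.4 and Protocol 13.2.9 without explanation.

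**Conclusion.** The point holds as a defect in a stated rule with a conditional consequence. The SAP makes length of follow-up depend on outcome, and the direction of any resulting bias is upward for Kaplan-Meier risks and annual rates.

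It would go too far to say that the rates are inflated. That needs exit to fall after the last attended visit and events in the gap to be recorded, and the documents establish neither. The bias is nil if the final visit is the exit. It is about 2-5% under assumed attendance of 80-90% with full capture of serious events, and about 10% or more only if attendance falls to 70% or below, or if most patients have a gap of months.

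At 75 patients, with descriptive results produced only if numbers are adequate, a shift of a few percent would not change a conclusion. The correction is still worth making because it is cheap and removes an ambiguity in the main secondary results.

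**What to change.** In SAP 7.2.2, remove the adverse-event option and set one end date for all secondary clinical endpoints that does not depend on adverse events:

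- the final-visit or study-exit date;
- death, if earlier;
- for subjects lost to follow-up, the last available contact date, in line with SAP 7.4.

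Count endpoint events only up to that same date, and record the change from Protocol 13.2.9 in SAP 7.12.

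The last-contact clause is needed. Under Protocol 9.10 a subject is declared lost only after a missed visit, a four-week wait and three failed contacts. If the exit form is dated then, running everyone to that date would credit unobserved months as event-free and bias rates downward.

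The cost is a sentence or two in the SAP and the matching line in the programming document; study exit is already recorded on an exit form. A few late events may drop out of the rates, though they stay in the safety listings, and the reported rates may be slightly lower.

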#### 4.2.2 Secondary Endpoints

1. To compare the two atrial ATP Programming arms in terms of clinical endpoints reported below:
  - all-cause death (at the end of 24 months), measured as time to event;
  - cardiovascular hospitalization (HF, AF or other), measured as time to first event and annual rate;
  - Annual rate for all-cause hospitalization;

- AT/AF burden metrics, measured in terms of time to first event (daily burden  $\geq 1$  day,  $\geq 2$  days,  $\geq 30$  days) or the ratio between time in AT/AF and the observation period;
  - number of successful and unsuccessful treated AT/AF episodes out of detected episodes;
  - number of delivered therapies per episode;
  - number of ATP sequences;
  - stroke, TIA or other thromboembolic events;
  - LA diameter (where available);
  - percentage of patients treated by anticoagulation therapy according management guideline;
  - electrical or pharmacological cardioversions, measured as time to first event and annual rate;
  - biventricular pacing percentage (in CRT-P /CRT-D patients).
2. Composite endpoint made of death, cardiovascular hospitalizations, stroke, TIA or other thromboembolic events;
  3. To evaluate the incidence of persistent AF in patients with sick sinus syndrome compared to the one found in the Minerva trial, and characterize the difference between the European and Indian populations;
  4. To evaluate the efficacy of atrial ATP therapies as a function of the device type (IPG, ICD, CRT-D, CRT-P), and population characteristics (baseline characteristics, implant indications).

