### 7.9.2 Secondary Endpoints

The time-to-event outcomes defined in section 4.1.2 will be summarized using Kaplan-Meier plots, tables with survival probabilities and 95% confidence intervals estimated using complementary log-log method, for each randomization group, if the number of followed-up patients and observed events will be adequate. Descriptive statistics will also be presented for the time-to-event outcomes. No formal hypothesis testing nor HR calculation is planned. Details about all time-to-event variables will be listed.

Counts and percentages will be used for categorical variables, for each randomization arm. Continuous variables will be summarized by descriptive statistics as described in the section 7.2.1.

Annual rates will be calculated for appropriate endpoints together with their 95% confidence interval (95%CI), for each randomization group, if the number of followed-up patients and observed events will be adequate.

Since the study was terminated early with small number of patients enrolled (less than 10% of expected sample size), the evaluation of persistent AF in patients with sick sinus syndrome compared to the one found in the Minerva trial, and the characterization the difference between the European and Indian populations, and the evaluation of the efficacy of atrial ATP therapies as a function of the device type (IPG, ICD, CRT-D, CRT-P), and population characteristics (baseline characteristics, implant indications) would not be robust: thus, the analyses will not be performed.

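### SAP 7.2.2 stops secondary-endpoint exposure at the event, and the SAP states no other person-time and no numerator for annual rates of repeatable events

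*SAP*

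**What the plan says.** SAP 4.2.2 asks for annual rates of three events that can recur:

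- "cardiovascular hospitalization (HF, AF or other), measured as time to first event and annual rate"
- "Annual rate for all-cause hospitalization", with no time-to-event version beside it
- "electrical or pharmacological cardioversions, measured as time to first event and annual rate"

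SAP 7.2.2 says that several secondary variables, including the "annual rate for all-cause hospitalization will be derived from the adverse event dataset and will be described in detail in the SPR". The next paragraph gives the only secondary exposure rule: "The exposure time (months) for the secondary endpoints will be computed from the date of randomization to the date of the notice" (a follow-up visit or an adverse event) "for patients without events or to the date of the specific event otherwise".

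SAP 7.9.2 then states: "Annual rates will be calculated for appropriate endpoints together with their 95% confidence interval (95%CI), for each randomization group", provided that numbers are adequate. It gives neither a numerator nor a person-time.

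Protocol 13.2.9 defines a time to event that stops at the event. Separately, it describes rates per 100 person-years from a Poisson model with a scale parameter for over-dispersion. It does not say when person-time ends.

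**The concern.** A clock that stops at the event is right for time to first event. For the annual rate of a repeatable event it removes time in which the patient is still observed and can be hospitalized or cardioverted again. The rule in 7.2.2 closely follows a sentence naming an annual rate and does not exclude rates. By contrast, the primary-endpoint rule in the same section is confined to one time-to-event measure: "The exposure time (months) for the time to first persistent AF will be computed from the date of randomization".

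At stake are the per-arm annual rates and their confidence intervals. All-cause hospitalization is the most exposed, because the annual rate is its only measure. The distortion depends on how many patients have an event and when, so it need not be equal in the two arms. A confidence interval would not reveal it, since the interval reflects sampling error and not the choice of denominator.

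**Working it through.** **Is another denominator given?** The documents state no figure for these rates, so there is none to reproduce. The candidate places in the text are:

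- SAP 7.2.2, primary rule: persistent AF only.
- SAP 7.4: censors the time to event at last contact; silent on rates.
- SAP 4.2.2: mentions an observation period, but as the denominator of AT/AF burden.
- SAP 7.9.2: annual rates with intervals; no numerator or person-time.
- Protocol 13.2.9: person-years and a Poisson model; no end of person-time.

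None supplies it. 7.2.2 also does not say which event stops the clock when a patient has several. The calculations below take the first.

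**Inputs.**

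- Event rate r: 0.025 and 0.089 per year, the heart failure hospitalization rates without and with progression of subclinical AF in Protocol 4.1.4. These come from another study and one cause of admission. Rates of 0.2 and 0.5 per year are assumed.
- Follow-up T: 1 and 2 years, assumed. A ceiling of 2.43 years follows from 26 February 2019 (protocol date) to 31 July 2021 (end of the final-visit window in SAP 5): 886 days / 365.25, assuming no enrolment before the protocol date.
- Between-patient variation: none, or gamma frailty with variance 1 (assumed).

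**Formulas**, as ratios to the true recurrent rate r:

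- A. All events over truncated time, common constant rate. Expected events are rT and expected time to first event or T is (1 − exp(−rT))/r. Ratio = rT / (1 − exp(−rT)).
- B. All events over truncated time, frailty. Expected truncated time is ln(1 + rT)/r. Ratio = rT / ln(1 + rT).
- C. First events over truncated time. With a common constant rate the ratio is 1. With frailty it is [1 − 1/(1 + rT)] / ln(1 + rT).

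| r per year | T (years) | A | B | C, frailty |
|---|---|---|---|---|
| 0.025 | 1 | 1.013 | 1.012 | 0.988 |
| 0.025 | 2 | 1.025 | 1.025 | 0.976 |
| 0.089 | 1 | 1.045 | 1.044 | 0.959 |
| 0.089 | 2 | 1.092 | 1.087 | 0.922 |
| 0.2 | 1 | 1.103 | 1.097 | 0.914 |
| 0.2 | 2 | 1.213 | 1.189 | 0.849 |
| 0.5 | 1 | 1.271 | 1.233 | 0.822 |
| 0.5 | 2 | 1.582 | 1.443 | 0.721 |

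Example: r = 0.5, T = 2 gives rT = 1, so A = 1/(1 − 0.368) = 1.582 and B = 1/0.693 = 1.443.

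At the ceiling with r = 0.089, rT = 0.216 and A = 0.216/0.194 = 1.112.

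**Staggered entry.** If follow-up is spread evenly from 0 to C = 2.43 years (assumed) with a common constant rate, the ratio is (rC/2) / [1 − (1 − exp(−rC))/(rC)]. This gives 1.020, 1.073, 1.168 and 1.442 for the four rates.

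**Between arms.** Take assumed true rates of 0.3 and 0.5 per year over 1.5 years, a ratio of 0.60. Formula A gives 0.373 and 0.711, a ratio of 0.52. Formula B gives 0.363 and 0.670, a ratio of 0.54.

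**Scale of sampling error.** The exact Poisson 95% interval for 10 events is 4.80 to 18.39, or 0.48 to 1.84 times the estimate.

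**The case against.** The strongest reply is that the rule was never meant for rates. It cannot apply literally to every secondary endpoint: LA diameter, biventricular pacing percentage and anticoagulation percentage have no event at which to stop. Some narrowing is unavoidable, and time to event is the natural one. SAP 3 asks that the plan be read with the protocol, and Protocol 13.2.9 keeps rates apart from time to event. SAP 7.2.2 also sends the derivation details to the SPR, which is not among the documents and may use full follow-up.

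This stands in part. A reader might infer that the sponsor plans to divide all events by truncated time. The documents do not show that: no passage gives the numerator, and the SPR is unseen. But 7.2.2 places the rule just after a named annual rate, and neither the rest of the SAP nor Protocol 13.2.9 supplies another denominator. An SPR using full follow-up would depart from 7.2.2 as written, and SAP 7.2.1 requires departures from the SAP to be described and justified.

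A second reply also stands: first events over time to first event is internally coherent. It is not an error in itself. It only fails to be the recurrent rate that the protocol's over-dispersed Poisson model suggests, and the SAP does not state which rate it wants.

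Finally, 58% should not be read as the expected bias. It needs an assumed 0.5 events per year, two full years of follow-up and no variation in risk between patients. Under the frailty model that yields the understatement in column C, the same case gives 44%.

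**Conclusion.** The point holds as a wording fault of minor severity: a stop-at-event rule with no exception for rates, and annual rates left without a stated numerator or person-time of their own. Whether a wrong denominator will actually be used is uncertain.

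If all events are counted over the truncated time, the overstatement is about 1 to 11% at the Protocol 4.1.4 rates. At assumed rates of 0.2 to 0.5 per year over 1 to 2 years it is about 10 to 58% with a common constant rate, or 10 to 44% under gamma frailty of variance 1. With around 10 events per arm, the bias at the Protocol 4.1.4 rates lies well inside sampling error, and even the larger figures do not exceed the upper Poisson limit.

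No trial conclusion turns on it. The study stopped with 75 patients, SAP 7.9.2 plans no test or hazard ratio, rates appear only if numbers are adequate, and SAP 7.12 defers the final decision on endpoint evaluation.

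**What to change.** In SAP 7.2.2, keep the current rule and limit it to the time-to-event measures: death, the composite, stroke/TIA/thromboembolic events, and first cardiovascular hospitalization or cardioversion. Naming the thromboembolic endpoint matters, because SAP 4.2.2 gives it no measure and it would otherwise lose its exposure rule. Then add: *For annual rates, all events are counted and divided by total follow-up from randomization to death, exit or last contact, regardless of events.* Align the SPR.

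If first-event incidence is what is wanted, the SAP should say so and label the result accordingly. If the SAP can no longer be amended, state the numerator and denominator used in the clinical study report.

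The cost is a short edit to 7.2.2 and, if the SPR lacks it, one derived exposure variable. No new data are needed.
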